## **Data Analysis Plan (Updated for 2nd NCE Period)**

First, descriptive analysis will be conducted to compute the means and standard deviations of all predictor and outcome variables listed in the Measures section. Means of baseline covariates, including age, sex, injury severity, recency of injury, verbal intelligence, anxiety, and prior VR gaming experience, will be compared using independent samples t-test between intervention and control groups. Due to the randomization, we expect that most of covariates will show non-significant differences between assignment groups. These variables will be considered balanced between groups and not included as covariates in the analyses that follow. For the covariates that are found imbalanced between groups (perhaps due to the small sample size, they will be controlled statistically in the analyses that follow. This approach will reduce the number of covariates in respective statistical models and maximize the statistical power of each proposed analysis.

Next, hypotheses for each specific aim will be evaluated.

- **Aim 1**
  - *H1.1 and H1.2* will be tested using a *multi-level model* where scores on VR tasks and NIHTB- CB tasks (H1.1) or BRIEF2 scores (H1.2) will serve as respective dependent variables. Study visit (pre, post, follow-up) will serve as a predictor that is nested within subjects and condition will serve as a between-subject predictor.
  - *H1.3* will be tested using a *multi-level model* where time (Day 1 – Day 30) is nested within subjects. The EMA-EF scores will be the DV, allowing each patient to have unique initial level and rate of change in daily EF across the 30-day period.
  - Multi-level models have been used in studies with sample sizes as small as single cases. Therefore, our study with a sample size of 15 will be sufficient to conduct multi-level modeling analyses. Furthermore, in all multi-level models for Aim 1, we will use the Kenward-Roger correction in degrees of freedom^2 to further minimize small sample size bias and prevent inflation of type I error rates in estimation.
- **Aim 2**
  - *H2.1* will be tested using the same approach as H1.1-H1.2 via *multi-level modeling*. Study visit (pre, post, follow-up) will serve as a predictor that is nested within subjects and condition will serve as a between-subject predictor. The only difference is that for this model CPT 3 scores will serve as DV.
  - *H2.2* will be tested using an *independent samples t-test* with BASC- 3 APS scores at follow-up as DVs and condition as the IV.
  - *H2.3* will be exploratory in nature due to the small sample size. It will be tested using the SPSS Macro for 95% bias-corrected bootstrap mediation analysis with condition as the IV, VR and NIHTB-CB scores at post-intervention/follow-up as mediators, and CPT 3, BASC-3 at follow-up as DVs for each model.
- **Aim 3**
  - *H3.1* will be tested using the same approach as H2.2 via *independent samples t-tests*. The only difference is that for this model PedsQL scores at follow-up will serve as DV.
  - *H3.2* will be similar to H2.3 and exploratory in nature. It be tested using the same mediation analysis as in H2.3, but with PedsQL scores at follow-up as DV instead.

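### Covariates are chosen by baseline t-tests between randomised arms: this does not maximise power, and it cannot be carried out in the H2.2 and H3.1 t-tests

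*SAP*

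**What the plan says.** The first paragraph of the SAP's Data Analysis Plan lists the variables ("Means of baseline covariates, including age, sex, injury severity, recency of injury, verbal intelligence, anxiety, and prior VR gaming experience") and says that they "will be compared using independent samples t-test between intervention and control groups". It expects that "most of covariates will show non-significant differences between assignment groups", and continues: "These variables will be considered balanced between groups and not included as covariates in the analyses that follow". For covariates found imbalanced, "they will be controlled statistically in the analyses that follow". The reason given is: "This approach will reduce the number of covariates in respective statistical models and maximize the statistical power of each proposed analysis". No significance level is stated for the screen, and no covariate is named in advance on prognostic grounds.

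Under Aim 2, H2.2 is an independent samples t-test "with BASC- 3 APS scores at follow-up as DVs and condition as the IV". Under Aim 3, H3.1 uses the same test with PedsQL as the outcome. H1.1, H1.2 and H2.1 use multi-level models with visit and condition as predictors. On size, the SAP states that "our study with a sample size of 15 will be sufficient to conduct multi-level modeling analyses", whereas the protocol (Research Design and Methods) plans 32 children.

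**The concern.** A covariate earns its place in a randomised comparison by predicting the outcome, not by differing between arms. A baseline t-test in a correctly randomised trial tests a null hypothesis known to be true, so what it flags is chance. A prognostic variable that happens to look similar in the two arms is dropped and its gain in precision is lost. A variable unrelated to outcome may be kept, and because it is imbalanced it is collinear with treatment and costs precision. At this sample size, failing to reach significance is also very weak evidence of balance.

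What is at stake is power in the follow-up comparisons, a model that depends on chance baseline differences, and two hypotheses (H2.2, H3.1) for which the plan does not define the analysis once a covariate is flagged.

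**Working it through.** **Inputs from the documents.** At least seven screened variables; N = 15 (SAP) or 32 (protocol); 1:1 allocation (protocol, Visit 1).

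**Assumptions, because the documents give no figure.** Two-sided 5% for the screen and the outcome tests; 7 v 8 (or 16 v 16); normal data; seven independent covariates, one of which correlates r with the outcome; true effect 1 SD. The plan has no power figure to reproduce, so its verbal claim was tested directly.

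**1. What the screen can detect.** Smallest flagged difference = t(0.975, N − 2) × √(1/n₁ + 1/n₂).
- N = 15: 2.160 × √(1/7 + 1/8) = 2.160 × 0.5175 = 1.12 SD. If age is uniform over 6 to 17, its SD is √((12² − 1)/12) = 3.45 years, so the arms must differ by 1.118 × 3.45 = 3.86 years.
- N = 32: 2.042 × √(1/16 + 1/16) = 2.042 × 0.3536 = 0.72 SD.

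At N = 15, about 30% of variables called balanced still differ by more than 0.5 SD (0.299 in 400,000 draws).

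**2. Chance flags.** P(at least one of seven) = 1 − 0.95⁷ = 0.302; expected number 7 × 0.05 = 0.35. With pairwise correlations of 0.3 to 0.6 the probability falls to 28% to 21%.

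**3. Power for a single-visit comparison (the H2.2/H3.1 form).** 40,000 simulated trials per setting, power in %:

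| N | Strategy | r = 0 | r = 0.3 | r = 0.5 | r = 0.7 |
|---|---|---|---|---|---|
| 15 | SAP rule | 38.7 | 38.8 | 39.0 | 39.5 |
| 15 | No adjustment | 43.1 | 43.2 | 43.4 | 43.2 |
| 15 | Prognostic covariate fixed in advance | 40.2 | 43.4 | 50.8 | 66.5 |
| 15 | All seven | 21.3 | 22.8 | 26.5 | 35.9 |
| 32 | SAP rule | 75.5 | 76.0 | 76.6 | 77.3 |
| 32 | No adjustment | 78.2 | 78.3 | 78.4 | 78.2 |
| 32 | Prognostic covariate fixed in advance | 76.6 | 80.6 | 87.4 | 96.4 |
| 32 | All seven | 66.0 | 70.3 | 78.0 | 90.9 |

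The rule is below no adjustment in every column, by 3.7 to 4.4 points at N = 15 and by 0.9 to 2.7 at N = 32. With covariates correlated 0.3 or 0.6 among themselves (N = 15, 10,000 trials each) the loss was 2.5 to 3.6 points (for example 40.2 v 42.7, and 39.3 v 42.9). At N = 15 the SD of the estimate was 0.54 to 0.57 under the rule and 0.52 unadjusted. With one fixed covariate it ran from 0.54 (r = 0) to 0.39 (r = 0.7).

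**4. Bias and error rate.** Every strategy averaged 1.00 to 1.02 against a true effect of 1. Overall type I error of the rule was 3.9 to 5.1%. Conditional behaviour differs. In trials where the prognostic covariate is flagged but the plain t-test is still run, type I error is about 16% at r = 0.5 and 30 to 32% at r = 0.7, against about 5% if it is adjusted for.

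**5. Multi-level models.** In a REML random-intercept model (15 subjects, three visits, complete data, 30 data sets), adding a subject-level covariate changed the follow-up-by-condition estimate by at most 3 × 10⁻¹⁵ and its SE by a relative 10⁻⁵. In a further example the visit-by-condition SE stayed at 0.356, while the SE of the condition main effect fell from 0.425 to 0.311. So for change contrasts (H1.1, H2.1) covariate selection neither gains nor loses power, and for an overall condition effect a prognostic covariate matters. H1.3 was not assessed.

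**6. The two instructions side by side.** The general rule adjusts for flagged covariates in all later analyses. H2.2 and H3.1 are later analyses, but their named test takes condition and nothing else. No ANCOVA or regression fallback is given.

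**The case against.** The strongest reply is about weight. The trial seeks preliminary efficacy, the rule neither biases the estimate nor inflates overall type I error, and its loss against no adjustment is a few points. At N = 32 the loss is under 3 points, and it reversed when all seven covariates were modestly prognostic (r = 0.36 each: rule 80.5%, none 78.9%). This stands, and it limits the severity of the point.

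The power sentence can also be read as a comparison with entering every covariate. At N = 15 the rule does win that comparison (39.0% v 26.5% at r = 0.5), so keeping covariates few is sound. The defence is not general: at N = 32, all seven beat the rule at r = 0.5 and r = 0.7.

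The gain from a fixed covariate assumes that the right one is known. A non-prognostic choice gave 40 to 41% at N = 15, against 39% for the rule and 43 to 44% unadjusted. With several prognostic covariates the gain over no adjustment was only 2 to 3 points. This stands too. Even so, one fixed covariate matched or beat the rule in every setting tried.

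Adjusting when a prognostic variable is flagged does protect the error rate in those particular trials. That is a real benefit, but fixing the covariate in advance gives the same protection.

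Finally, adding a covariate to a two-group t-test would ordinarily mean ANCOVA. That is a reasonable guess at the intent, but the plan names the test and its only independent variable, and the choice would otherwise be made after the arms had been compared. The result for H1.1 and H2.1 also assumes a visit-by-condition term, which the SAP does not write out.

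**Conclusion.** The concern holds. Selection by baseline significance tests is explicit in the SAP, the statement about power is not correct, and the rule cannot be executed as written in H2.2 and H3.1.

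The practical loss falls on single-visit comparisons between arms: H2.2, H3.1, and H1.2 if it is read as a difference at follow-up. Against no adjustment it is about 2.5 to 5 points at N = 15 over all the runs, smaller at N = 32, and it may vanish or reverse in other settings. Against a well-chosen fixed covariate at N = 15 it is about 12 points at r = 0.5 (50.8 − 39.0) and 27 at r = 0.7 (66.5 − 39.5). At N = 15 a fixed covariate gains nothing over no adjustment at or below about r = 0.3.

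These sizes rest on the assumed alpha, effect and correlations. The qualitative conclusion is the same at both stated sample sizes. This should be corrected, but it does not by itself invalidate the trial.

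**What to change.** - Delete the baseline significance tests and the sentence claiming maximum power. Report baseline characteristics by arm descriptively, without p-values.
- For H2.2 and H3.1, replace the t-test with ANCOVA on one, at most two, covariates named in advance for expected prognostic strength and kept whatever the observed balance. Use the baseline score of the same measure if it is collected. The protocol names BASC-3 and PedsQL only at follow-up, and the Measures section that the SAP refers to was not in the text reviewed. Otherwise consider injury severity, or age if scores are not age-normed.
- If no covariate is expected to correlate with outcome above about 0.3, prespecify the unadjusted analysis.
- In the multi-level models (H1.1, H1.2, H2.1), keep the pre-visit score as part of the outcome, do not also enter it as a covariate, and do not select covariates by baseline tests.
- Present any further adjustment, including for a striking chance imbalance, as a sensitivity analysis.

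The cost is SAP wording, one or two degrees of freedom in H2.2 and H3.1, and about 3 power points at N = 15 if the chosen covariate proves unrelated to outcome (43.1 − 40.2 = 2.9 at r = 0).

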**PARTNERS HUMAN RESEARCH COMMITTEE
PROTOCOL SUMMARY**

Answer all questions accurately and completely in order to provide the PHRC with the relevant information to assess the risk-benefit ratio for the study. Do not leave sections blank.

PRINCIPAL/OVERALL INVESTIGATOR

[name]

PROTOCOL TITLE

Virtual Reality-based Rehabilitation for Children with Traumatic Brain Injuries

FUNDING

National Institutes of Health

VERSION DATE

Version 5.0 3/22/23

SPECIFIC AIMS

Concisely state the objectives of the study and the hypothesis being tested.

The overall goal of the project is to assess the preliminary efficacy of a novel VR-based interactive cognitive training (VICT) program for cognitive rehabilitation in children with TBI.

Aim 1. Examine VICT's efficacy in improving core and daily EF skills among children with TBI.

Hypothesis 1.1: Children in the intervention group will show enhanced improvement over controls in trained VR-based EF tasks and untrained NIH Toolbox tasks from baseline to post-intervention and follow-up visits;

Hypothesis 1.2: The intervention group will show better reported daily EF than controls at the follow-up visit;

Hypothesis 1.3: Children in the intervention group will show faster improvement than controls in daily-reported EF skills between post-intervention and follow-up visits.

Aim 2. Examine VICT's efficacy in reducing attentional problems among children with TBI.

Hypothesis 2.1: Children in the intervention group will show a greater reduction in attentional problems as measured by testing on the Conners Continuous Performance Test 3rd Edition™ (Conners CPT 3™) from baseline to the post-intervention and follow-up visits than controls;

Hypothesis 2.2: Children in the intervention group will show fewer everyday attentional problems on the Behavior Assessment System for Children 3rd Ed (BASC-3) self- and parent-ratings of attention at the follow-up visit than controls;

Hypothesis 2.3: The direct effect of the VICT program in reducing attention problems will be mediated by children's EF behaviors as measured by the Behavior Rating Inventory of Executive Function, Second Edition (BRIEF2) at the follow-up visit.

Aim 3. Examine VICT's efficacy in improving HRQOL among children with TBI.

Hypothesis 3.1: The intervention group will show higher levels of reported HRQOL than controls at follow-up;

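### The SAP's H1.3 model has no condition term and so contains no arm comparison; its models for H1.1, H1.2 and H2.1 include condition but do not specify the condition-by-visit term or the contrast to be tested

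*SAP*

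**What the plan says.** The comparisons are stated in the protocol under Specific Aims.

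- H1.1 expects "enhanced improvement over controls in trained VR-based EF tasks and untrained NIH Toolbox tasks from baseline to post-intervention and follow-up visits". H2.1 is of the same kind, for the continuous performance test.
- H1.2 reads "The intervention group will show better reported daily EF than controls at the follow-up visit".
- H1.3 reads "Children in the intervention group will show faster improvement than controls in daily-reported EF skills between post-intervention and follow-up visits".

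The endpoint paragraph under Research Design and Methods defines efficacy as change in the VR, NIH Toolbox and BRIEF2 scores, from baseline to post-intervention and from baseline to follow-up.

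The models are in the SAP's Data Analysis Plan.

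- H1.1 and H1.2 share one multi-level model: "Study visit (pre, post, follow-up) will serve as a predictor that is nested within subjects and condition will serve as a between-subject predictor".
- H2.1 "will be tested using the same approach as H1.1-H1.2 via" multi-level modelling, with only the outcome changed.
- H1.3 has days 1 to 30 nested within child: "The EMA-EF scores will be the DV, allowing each patient to have unique initial level and rate of change in daily EF". Condition does not appear in that bullet.
- For H2.2, by contrast, the SAP names "APS scores at follow-up as DVs and condition as the IV", and it also names condition for H2.3.

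**The concern.** Each of these hypotheses is a comparison between arms, so each needs a named coefficient or contrast that carries it.

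For H1.3 there is none. Random slopes let children differ from one another; they do not test whether the arms differ. A pre-specified hypothesis is left without a pre-specified test.

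For H1.1, H1.2 and H2.1 the arm term is present, but one sentence serves both a change hypothesis and a follow-up-level hypothesis, and these need different contrasts. If the contrast is not fixed in advance, it can be chosen after the data are seen. These models carry the protocol's endpoint and, with H1.3, all of Aim 1. The SAP labels only H2.3 and H3.2 exploratory, so these hypotheses stand as tests.

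**Working it through.** The documents available give no alpha, power, SD or effect size for these models, so there is no planned figure to reproduce. The check sets each hypothesis against its model and then illustrates the size.

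**Hypothesis against model**

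| | Protocol asks for | SAP model contains | Not stated |
|---|---|---|---|
| H1.1, H2.1 | arm difference in change to post and to follow-up | visit, condition | condition × visit; contrasts; how they combine |
| H1.2 | arm difference at follow-up | visit, condition | the follow-up contrast |
| H1.3 | arm difference in daily slope | day; child intercept and slope | condition; condition × day |

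**H1.3.** The written model is y = (b0 + u0) + (b1 + u1) × day + error, where u0 and u1 vary by child. The only fixed slope, b1, is pooled over arms. Take assumed slopes of 0.03 (8 intervention children) and 0.01 (7 controls). The pooled slope is then 0.01 + 0.02 × 8/15 = 0.0207, and simulated fits gave 0.020. Two arms that both improved at 0.0207 would give the same answer. With condition × day added, the fits recovered the arm difference: 0.020, truth 0.020. (That the pooled slope and the difference are close in value is an accident of the slopes chosen.)

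**Literal main-effects reading of H1.1, H1.2 and H2.1.** With balanced data, no arm difference at baseline and an effect D at both later visits, the condition coefficient estimates (0 + D + D)/3 = 0.67 D. This needs no assumed SD or correlation.

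For power, assume the SAP's 15 children split 7 versus 8, SD 1, equal within-child correlation rho, complete data, two-sided alpha 0.05 and D = 1 SD. Let f = √(1/7 + 1/8) = 0.518.

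- Main effect: SE = f × √((1 + 2rho)/3), 13 df. At rho 0.5 the SE is 0.518 × 0.816 = 0.423 and the noncentrality 0.667/0.423 = 1.58. Power is 31% at rho 0.5 and 25% at rho 0.8.
- Single-visit condition × visit contrast: SE = f × √(2(1 − rho)), 26 df. At rho 0.5 the SE is 0.518 and the noncentrality 1/0.518 = 1.93. Power is 46% at rho 0.5 and 84% at rho 0.8.

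**Combining the two visits (H1.1, H2.1).** Both change contrasts share the baseline score. Each has variance proportional to 2(1 − rho) and their covariance is proportional to (1 − rho), so their correlation is 0.5 whatever rho is. Simulation with no effect at either visit, rho 0.5 to 0.8:

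- better of the two reported: about 9% false positives per outcome;
- both required: about 5% + 5% − 9% = 1%, confirmed by simulation;
- each tested at 0.025: 4.5 to 4.7%;
- pre-named average of the two: 4.9 to 5.1%.

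The average has 57 to 92% power at D = 1 SD. If the effect halves by follow-up, it has 44% at rho 0.6, against 55% for the post contrast alone.

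**Baseline adjustment.** A chance baseline gap has a standard error of 0.518 SD. It shifts an unadjusted change contrast by −(1 − rho) times the gap, which at rho 0.6 is −0.40 × 0.518 = −0.21 SD for a one-SE gap. It shifts a baseline-adjusted contrast by essentially nothing. Simulated power for the follow-up visit at D = 1 SD:

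| rho | 0.5 | 0.6 | 0.7 | 0.8 |
|---|---|---|---|---|
| baseline-adjusted | 51% | 57% | 66% | 81% |
| unadjusted | 46% | 55% | 67% | 84% |

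The adjusted single-visit analysis has 12 df (by formula) and the unadjusted one 26, so the comparison is not like for like. A joint model with a common baseline mean was not evaluated.

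**The case against.** The strongest reply is that for H1.1, H1.2 and H2.1 the interaction is implied. The SAP never calls the model additive, condition is in it, and the protocol makes the intended comparisons plain. This stands. A reader might infer that the SAP plans the wrong model for these three hypotheses, or that the trial will run at 25 to 31% power. The documents support only that the term and contrast are not specified; those powers and the 0.67 D apply only if the main effect is taken as the test.

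Second, the protocol does name both change contrasts and joins them with 'and'. This also stands: what is missing is the rule that combines them. A reader might infer a 9% false-positive rate, but that arises only if the better result is reported. If 'and' means both must succeed, the rate is about 1% when there is no effect at either visit.

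Third, baseline adjustment is not needed to match a change endpoint, because randomisation leaves the unadjusted change contrast unbiased. This stands, and the power figures show no consistent gain. Adjustment is a recommendation, not a correction.

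None of this reaches H1.3. An analyst may guess that condition was meant, but the bullet omits it while the other between-arm analyses of Aims 1 and 2 name it. The Kenward-Roger correction planned for Aim 1 addresses small-sample inference and cannot supply a missing term.

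**Conclusion.** H1.3 is wrong as written and must be fixed. The model yields a pooled slope and no test of the stated hypothesis, and this conclusion rests on no assumption.

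H1.1, H1.2 and H2.1 are under-specified and should be clarified. Read literally as main effects, the condition coefficient averages in the pre-randomisation visit and estimates two thirds of an effect present at both later visits. Read as the protocol intends, the open matter is the contrast and, for H1.1 and H2.1, the combining rule, which moves the false-positive rate between about 1% and about 9% per outcome. H1.2 has a further loose end: the hypothesis concerns follow-up only, while the protocol's endpoint makes BRIEF2 change to both visits part of efficacy.

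The power and error rates are illustrations. SD, rho, alpha, effect size and the 7/8 split are assumptions; the total comes from the SAP ("our study with a sample size of 15 will be sufficient to conduct multi-level modeling analyses"), whereas the protocol plans 32. Part of the SAP document ahead of the Data Analysis Plan was not available for review, nor was the Measures section to which it refers. The analysis plan for these hypotheses was.

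**What to change.** Amend the SAP before unblinded analysis.

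- **H1.3 (must fix).** Add condition and condition × day to the model with child-specific intercepts and slopes, and name condition × day as the test.
- **H1.1 and H2.1 (should fix).** Fit categorical visit, condition and condition × visit. Name the post-intervention and follow-up contrasts and state how they combine: both required, either one with Holm, or their average. The average is the stronger choice only if the effect is expected to last to follow-up.
- **H1.2 (should fix).** Name the follow-up contrast from the same model, and reconcile it with the protocol's endpoint paragraph on BRIEF2 change to both visits.
- **Optional.** Use a common baseline mean, or the baseline score as covariate, where a baseline score exists. This removes the effect of chance baseline gaps. With 15 children, single-visit power is higher at rho 0.5 to 0.6 and about equal or slightly lower at 0.7 to 0.8.

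The cost is SAP wording. The data, the visits and the kind of model stay the same.

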- Intervention session can take place any time following the baseline assessment. Participants will be provided a tutorial to be familiar with the VR equipment, as well as a standardized interactive tutorial automatically built into the VR for completing the training tasks.
 - The VR game for the intervention group is called “Rescue the Lubdubs”. In this game, children will try to rescue an animated creature called “lubdub” by defeating the guards (training inhibitory control skills), memorizing the passcode to unlock castle gates (training working memory skills), and matching partners between the lubdub’s belly and its guards (training cognitive flexibility skills).
 - The VR game for the control group is a relaxing and immersive playground where children can throw projectiles (bees, beans, etc.) to different objects in the virtual environment (moving boards, water buckets, light bulbs, etc.). This game does not require the use of any of the executive functioning skills (i.e., inhibitory control, working memory, cognitive flexibility) and therefore serves as a placebo game for the control group.
- Participants will only be randomized to either intervention or control groups after completion of the baseline assessment. The randomization scheme is designed blocked randomization with random block sizes of 2 and 4 and 1:1 ratio for intervention and control treatment.
 - Randomization and the intervention session will be completed by an unblinded Research Assistant.
- Participants will then complete at least one (1) 30-minute intervention session. The child and their family can decide if they would like to play the game for a longer period of time. Breaks are permitted upon patient request at any time. AEs and serious AEs will be actively monitored throughout the intervention sessions. Anxiety in anticipation of the intervention will also be assessed before the intervention, while simulator sickness, perceived exertion, and subjective VR experience will be measured after the intervention.

Visit 2:

Post Intervention Assessment: Post-intervention assessment will be scheduled upon completion of the intervention session and should take place within 1 week after the intervention session. Research staff blinded to the participants’ group assignment will administer the post-training assessment, which consists of the same set of tasks as those in

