the baseline assessment, as well as VR experience questions such as motion sickness, perceived benefits and challenges, and physical exertion.

Between Visit 2 and Visit 3:

- A brief EMA-EF Survey will be sent to participants to complete daily between the post-intervention and follow-up visits, which may take about 2 minutes per day for 30 days.

Visit 3:

Follow-Up Visit

- Follow-up visits are scheduled 30 days following the post-intervention assessment (up to 12 months). Staff blinded to the participants' group assignment will administer the following measures:
 - VR and NIH Toolbox tests;
 - Conners CPT 3;
 - Children's Anxiety Meter;
 - Self-report BRIEF2, BASC-3, and PedsQL Generic Core Scales;
 - TPVT
 - Media Use Survey.
 - A parent will complete the parent-report version of BRIEF2, BASC-3, and PedsQL.

The study endpoint is the preliminary efficacy of the VICT program, defined as the changes in VR Assessment Scores, NIH Toolbox Composite Scores, and BRIEF2 Global Scores between baseline and post-intervention and between baseline and follow-up assessment.

For studies involving treatment or diagnosis, provide information about standard of care at Partners (e.g., BWH, MGH) and indicate how the study procedures differ from standard care. Provide information on available alternative treatments, procedures, or methods of diagnosis.

The virtual reality intervention is designed to be supplementary to standard of care at Spaulding Rehabilitation Hospital. Therefore, all participants will still receive standard of care as determined by their doctors regardless of participation of this study or random assignment to the intervention or control group.

Describe how risks to subjects are minimized, for example, by using procedures which are consistent with sound research design and which do not unnecessarily expose subjects to risk or by using procedures already being performed on the subject for diagnostic or treatment purposes.

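### H1.3 compares the arms only on rate of change in a diary that begins after the intervention, so on its own it cannot show whether VICT improved daily EF

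*SAP*

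**What the plan says.** Protocol, Specific Aims, states H1.3 as a rate hypothesis: "Children in the intervention group will show faster improvement than controls in daily-reported EF skills between post-intervention and follow-up visits". Aim 1, to which it belongs, asks whether VICT improves core and daily EF skills.

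The timing is in the protocol's Research Design and Methods. Under Visit 1, Intervention Session: "Participants will then complete at least one (1) 30-minute intervention session". The post-intervention assessment (Visit 2) "should take place within 1 week after the intervention session". Only then does the diary begin: "A brief EMA-EF Survey will be sent to participants to complete daily between the post-intervention and follow-up visits". Its planned length is 30 daily surveys. No diary before the intervention is described.

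The SAP's Data Analysis Plan, Aim 1, gives H1.3 a multi-level model "where time (Day 1 – Day 30) is nested within subjects", with EMA-EF as dependent variable, "allowing each patient to have unique initial level and rate of change in daily EF across the 30-day period". That bullet does not name condition, a condition x day term, or any between-arm comparison of diary level. The bullet for H1.1 and H1.2, by contrast, does name the arm: "condition will serve as a between-subject predictor".

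**The concern.** The intervention is over before the first diary entry. If it changes daily EF at all, some or all of the change may already be there on Day 1. A comparison of slopes sees only how the arm difference moves from Day 1 to Day 30, not how large it is. A gain that is present and stays is invisible to it. A gain that is present and wears off makes the slope difference negative, although the intervention arm is at no time worse than control. Only a gain that keeps growing after Visit 2 registers in favour.

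A slope difference reported alone is therefore ambiguous. A null result fits both no effect and a lasting effect, and a negative result fits both a deterioration and a benefit that fades. The data to separate these are collected, but the plan does not say that they will be used for it.

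**Working it through.** The documents give no effect size, SD, alpha or power for H1.3, so there is no planned figure to reproduce. The check has two parts: algebra that needs no assumptions about variance, and an illustration that does.

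**Algebra.** Let D(t) be the true arm difference on day t, positive when the intervention arm is better. With complete diaries the condition x day coefficient estimates the least-squares slope of D(t),

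sum of (t − 15.5) D(t) / sum of (t − 15.5)², with denominator 30 × (30² − 1)/12 = 2247.5.

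- Constant D: the numerator is zero, so the expected slope difference is 0.
- D falling linearly from D1 to D30: the coefficient is (D30 − D1)/29, which is negative.
- D rising linearly from 0: the coefficient is positive.

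**Illustration: inputs.** From the documents: 30 days (protocol, Between Visit 2 and Visit 3), n = 15 (SAP, Aim 1) and 1:1 allocation (protocol, Intervention Session), taken as 8 v 7. The protocol's 32 children, taken as 16 v 16, are shown for comparison. Assumed: child SD 1, daily SD 1, slope SD 0.02 per day, two-sided 0.05, higher score = better EF, complete diaries, independent daily errors. With balanced complete data the mixed-model contrasts reduce to t-tests on each child's slope and mean, with n − 2 degrees of freedom.

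**Slope test, 8 v 7.**
- SD of a child's fitted slope: √(0.02² + 1/2247.5) = 0.0291.
- SE of the arm difference: 0.0291 × √(1/8 + 1/7) = 0.0150; critical t on 13 df is 2.16.
- Sustained 0.8 SD gain: expected difference 0, so a favourable result in 2.5% of trials, the chance rate.
- 0.8 SD fading to 0: expected difference −0.8/29 = −0.0276; noncentrality −0.0276/0.0150 = −1.83; significantly negative in about 40% and significantly positive in practically none.

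**Mean-level test, 8 v 7.**
- SD of a child's 30-day mean: √(1 + 1/30) = 1.017; SE of the arm difference 1.017 × 0.5175 = 0.526.
- Sustained 0.8 SD: noncentrality 0.8/0.526 = 1.52; power about 30%.
- Fading 0.8 to 0: average difference 0.4; noncentrality 0.76; power about 10%, with a significantly adverse result in about 0.5% or less.

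**Sensitivity of the negative-slope rate, 8 v 7.**

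| Change to the fading case | Significantly negative slope |
|---|---|
| Base: 0.8 SD to 0, slope SD 0.02 | about 40% |
| Slope SD 0.01 | 56% |
| Slope SD 0.04 | 19% |
| Day-to-day autocorrelation 0.5 | 24% |
| Gain of 0.5 SD, fading to 0 | 19% |
| 0.8 SD gain that only halves | 13% |
| Gain of 0.3 SD, fading to 0 | 9% |

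**With 16 v 16** and the base inputs, the negative-slope rate is 74%. The mean-level test finds a sustained 0.8 SD gain in about 58% and the fading gain in about 18%.

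**The case against.** The strongest reply is that the investigators chose a rate hypothesis and are entitled to it. It fits an expectation that tested skills improve first and daily behaviour diverges later. If the benefit fades, faster improvement than controls is simply false, and a negative slope answers H1.3 correctly. That stands, and is why the slope test should stay. It does not remove the ambiguity when Aim 1's broader question is asked of the same diary.

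Second, level of everyday EF is already analysed. The SAP models BRIEF2 over the three visits with condition as a predictor, and the protocol's endpoint includes BRIEF2 change from baseline. This also stands. It confines the point to the diary, and EMA-EF is not part of the endpoint definition.

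Third, the H1.3 model already gives each patient an initial level. It does, but as a patient-specific effect. No comparison of that level between arms is planned.

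Fourth, the percentages rest on assumed inputs, and a 0.8 SD daily-EF gain is a generous assumption where the minimum dose is one 30-minute session. True. The percentages move with the inputs, but the signs do not.

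Two stronger readings are tempting and are not supported. A reader might infer that H1.3 conflicts with H1.1, because H1.1 expects gains by the post-intervention visit. But H1.1 concerns VR and NIH Toolbox task scores and predicts nothing about the diary. A reader might also infer that the plan would count a fading benefit as harm. Nothing in either document labels a lower slope that way; the plan is only silent on how to read one.

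**Conclusion.** The point holds in a limited form. As planned, H1.3 cannot detect a daily-EF benefit that is present from Day 1 and sustained, and its expected value is negative for one that fades. This follows from the diary's timing and the form of the contrast, and needs no assumed variance. The size is illustrative only: in the base case, about 2.5% detection by slope against 30% by mean level for a sustained gain, and a significantly negative slope in about 40% for a gain fading to zero. The latter ranges from 9% to 56% over the alternatives tried. Missing diary days were not modelled.

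The consequence is for what the diary can conclude about daily EF. The trial's defined endpoint is unaffected. It is a worthwhile, inexpensive improvement to the SAP.

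**What to change.** In the SAP's H1.3 bullet:

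- Name the fixed effects: condition, day and condition x day, with day centred at the middle of the 30 days. The condition coefficient is then the arm difference in mean 30-day level under the linear model.
- Keep condition x day as the H1.3 test.
- Report the arm difference in mean level, with its confidence interval, beside it as a supporting contrast.
- State in advance that the slope difference is interpreted together with the level difference, so that a lower slope with a higher level is described as consistent with a fading benefit.

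This uses the same data and the same model, and changes SAP wording only. The cost is one extra reported contrast with low power at n=15: about 30% for a sustained 0.8 SD gain and about 10% for a fading one. Its main value is therefore the estimate and interval that put the slope in context. Because the diary has no pre-intervention days, that level difference rests on randomisation alone and cannot be expressed as change from a diary baseline.
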